- Determine whether tamoxifen-resistance and fulvestrant-sensitivity gene expression signatures are observed in patients with cyclinD1 overexpressing breast cancers.
 - A gene signature that distinguishes cells that are responsive to tamoxifen and those that are resistant to tamoxifen has been established using cell lines in vitro. Similarly, a gene signature of the same cells in response to fulvestrant was also determined. Using these signatures obtained in vitro, we will compare whether the same gene signature characterizes tumors that are resistant or sensitive to tamoxifen and fulvestrant respectively in patients samples using selected gene by nanostring analysis by RNA extraction from paraffin embedded sections.
- Determine whether patient's response to tamoxifen or fulvestrant correlates with the response of their primary cells in vitro.
 - The organoid core facility has recently developed a method by which cells from primary tumors from patients can be grown in vitro. When samples are available for culture in vitro, we will test whether the cells derived from individual patients respond the same as the tumor in vivo in the same patient. For this experiment, cells in culture will be treated with the same drug (tamoxifen or fulvestrant) as the patient has received. We will conduct standard proliferation assays (MTT) assay over a range of doses of the drug as we are aware that intratumoral doses achieved clinically and doses in vitro can be quite different. If successful this analysis would validate the use of such organoid culture to predict patient response in the future. Therefore, we view this analysis as an opportunity to determine proof of principal of such technique and may have wide impact for several studies in the future.

Statistical Analysis Plan

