Robertson et al (2007) gave a mean change from baseline in Ki67 of a 2.8% decline and a standard deviation of 22.5% of cells staining for Ki67 for patients receiving fulvestrant 250 mg. In the placebo group they reported a mean reduction and standard deviation of 7.1% +/- 18.0%. There was no significant difference ($p=0.97$) between groups. In the present study, we hypothesize that for women with cyclin D1 overexpression, high dose fulvestrant will have a higher mean reduction in Ki67 than tamoxifen. 58 patients (29 patients in each study treatment arm) will be required to detect a difference between treatments of 15% in cells staining for Ki67 (mean reduction from baseline of 5% for Ki67 level in the tamoxifen group vs. 20% in the fulvestrant group) with power 0.80 for a two-sided test at the 0.05 level. We estimate that 10% of those enrolled to the tamoxifen arm may dropout from the study; however, since fulvestrant is given as a one-time dose, we do not expect attrition from this arm of the study. To account for drop-outs 32 patients will be randomized to each arm.

Treatment assignment

Comparison in the Change of Proliferation Index between Fulvestrant and Tamoxifen in Cyclin D1 +, Estrogen Receptor + Breast Cancer

[name], PI

Essential Elements

#13, 09/13/2017

A total of 64 patients will be randomized in a 1:1 allocation (32 patients to the tamoxifen arm and 32 to the fulvestrant arm) stratified by menopausal status (pre vs. post).. Randomization will be initiated at Mount Sinai by the research pharmacy, using separate randomization lists for pre and post menopausal patients..

Endpoints

Primary endpoint:

- The change in proliferation index between core biopsy and definitive surgery as measured by the percentage of cells staining for Ki67 in each treatment arm, stratified by menopausal status.

Secondary endpoints:

- Determine whether there is a differential treatment effect between tamoxifen and fulvestrant for pre and post menopausal patients.
- The change in estrogen receptor and progesterone receptor levels between core biopsy and definitive surgery in patients treated with fulvestrant or tamoxifen.
- Determine whether tamoxifen-resistance and fulvestrant-sensitivity gene expression signatures are observed in patients with cyclinD1 overexpressing breast cancers.
- Determine whether patient's response to tamoxifen or fulvestrant correlates with the response of their primary cells in vitro.

Data Analysis:

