An intent to treat analysis will be applied to this study. All primary and secondary analysis will be performed, stratified by menopausal status(pre vs. post). Primary continuous response rate of percentage of cells staining for Ki67 between treatment groups will be analyzed using stratified analysis of covariance (ANCOVA). Treatment groups will be compared by stratified analysis of covariance with respect to the outcome variable of post treatment percentage of cells staining for Ki67 with covariate baseline percentage of cells staining for Ki67, allowing for estimation of the mean change from baseline. Assumptions underlying ANCOVA will be evaluated. Transformation of the data will be undertaken if appropriate. A treatment diary will be used for patients enrolled to the tamoxifen arm to record all treatment doses and to help account for any missing data.

A secondary analysis will be a per protocol analysis. Potential interaction will be tested for treatment by stratum (menopausal status) to determine if there exists a differential treatment effect for pre and post menopausal subjects. The mean change in levels (expressed as a percentage of cells staining positive within the breast tumor) of ER (and PR) between pre-treatment and post-treatment will be compared between treatment arms by ANCOVA stratified by menopausal status as in the statistical analysis of the primary objective.

Gene signatures that distinguish cells that are responsive and those that are resistant to tamoxifen have been established using cell lines in vitro. Gene signatures for responsiveness/resistance to fulvestrant have also been established. Presence of these gene signatures will be determined for all patients in this study. Patients having signatures for responsiveness or resistance to tamoxifen (fulvestrant) will be compared with respect to change in Ki67 after treatment with tamoxifen (fulvestrant) by stratified ANCOVA.

Comparison in the Change of Proliferation Index between Fulvestrant and Tamoxifen in Cyclin D1 +, Estrogen Receptor + Breast Cancer

[name], PI

Essential Elements

#13, 09/13/2017

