To determine whether patient's response to tamoxifen or fulvestrant correlated with response in their primary cells in vitro, cells from primary tumors from patients will be grown in vitro. Proliferation assays over a range of doses in vitro, of the same drug that the patient received will be conducted. Correlations between in vitro assay results and patient assay results will be examined by Pearson correlation or Spearman correlation for data not normally distributed for pre- and post-menopausal patients. Dose response will also be analyzed by regression analysis.

Stopping Rule:

Keeping in mind the potential proliferative effect of tamoxifen, this trial will include an early stopping rule, where if the mean change from baseline in the Ki67 proliferation index among the first fourteen patients in the tamoxifen arm is an increase of at least 25%, that arm of the trial will be terminated. Although fulvestrant is unlikely to cause acceleration of proliferation, the same stopping rule will be applied to the fulvestrant arm as well. A mean increase of 25% in 14 patients would give an 80% confidence interval that the true mean Ki67 increase in a treatment arm is in the range of 16% to 34%.

An additional stopping rule will be implemented based on the number of patients experiencing a high level of proliferation (50% or higher). If 2 of the first 10 patients in a treatment arm experience an increase from baseline in the Ki67 proliferation index of 50% or more, then that treatment arm will be terminated.

PATIENT ELIGIBILITY

Inclusion and Exclusion Criteria

Inclusion criteria:

- Written informed consent prior to beginning specific protocol procedures, including expected cooperation of the patients for the study treatment regimen and follow-up, must be obtained and documented according to the local regulatory requirements
- Adult women greater than 18 years of age
- Eastern Cooperative Oncology Group (ECOG) performance status (PS) 0-2
- New diagnosis of invasive cyclin D1 +, ER+, PR +/-, Her2- breast cancer
 - Cyclin D1 positive as defined as a total immunohistochemical score of 5 or greater
 - Hormone receptor positive as defined as $\geq 10\%$ positive stained cells
 - HER2-normal (IHC score 0-1 or FISH negative [in-situ hybridization (ISH) ratio ≤ 2.0 status])
- Tumor size at least 5 mm with planned primary surgery at Mount Sinai
- A negative urine dipstick pregnancy test

Exclusion criteria:

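### The correlation between culture response and patient response is split by menopausal status but not by drug, so a difference between the two drugs could pass for patient-level prediction

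*Combined protocol and SAP*

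**What the plan says.** The last secondary objective asks whether a patient's response to tamoxifen or fulvestrant correlates with the response of her own tumour cells in culture. Secondary Objectives describes the experiment: "cells in culture will be treated with the same drug (tamoxifen or fulvestrant) as the patient has received". Data Analysis repeats that proliferation assays over a range of doses "of the same drug that the patient received will be conducted".

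For the analysis itself, Data Analysis says that correlations "will be examined by Pearson correlation or Spearman correlation for data not normally distributed for pre- and post-menopausal patients". The general rule at the start of that section names the same single factor: "All primary and secondary analysis will be performed, stratified by menopausal status(pre vs. post". A closing sentence adds a regression analysis of dose response and does not mention arm.

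The gene-signature analysis, which comes just before, is written drug by drug: patients with signatures for one drug "will be compared with respect to change in Ki67 after treatment with tamoxifen (fulvestrant) by stratified ANCOVA". The correlation has no matching wording.

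Secondary Objectives and Correlative Laboratory Research both say that a successful result would validate organoid culture as a predictor of patient response.

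**The concern.** The question is about individuals: among women given the same drug, do those whose cells respond in culture also show the larger fall in Ki67? A correlation across both arms answers a mixed question, because part of it comes from the difference between the two drug means.

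The plan's own hypotheses point to such a difference on both axes. In patients it assumes a "mean reduction from baseline of 5% for Ki67 level in the tamoxifen group vs. 20% in the fulvestrant group". In the laboratory, Background and Rationale reports that cells overexpressing cyclin D1 are more sensitive to fulvestrant, whereas tamoxifen is said to amplify their growth signalling. If both hold, tamoxifen patients cluster at low response on both axes and fulvestrant patients at high response. The pooled correlation is then positive even if culture says nothing about which woman responds within either arm. Two drugs tested over their own dose ranges also need not share a read-out scale, which could add a further shift between drugs in either direction.

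What is at stake is the validation claim. A pooled correlation could appear to support it when the cultures show only that two drugs differ.

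**Working it through.** **Inputs from the documents**
- In vivo difference between arms: 20 − 5 = 15 points of Ki67 reduction.
- SDs of Ki67 change, from the cited 250 mg trial: a "standard deviation of 22.5% of cells staining for Ki67 for patients receiving fulvestrant 250 mg" and, for placebo, a "mean reduction and standard deviation of 7.1% +/- 18.0".
- 64 patients randomised 1:1; 58 evaluable patients (29 per arm) required.
- Cultures come only from tumours over 1 cm, and only when samples are available (Correlative Laboratory Research).

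**Assumptions**
- SD of Ki67 change about 20.
- Difference between drugs in the culture read-out, dx, of 0.5, 1 or 2 SD. No size is given in the documents.
- 10, 20 or 32 cultures per menopausal stratum. Equal strata would hold at most 64 / 2 = 32 patients each.
- Equal arms within a stratum, and no association within arms.

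**Step 1: is an SD near 20 consistent with the plan?** The root-mean-square of the two SDs is √((22.5² + 18.0²)/2) = √415.1 = 20.37. Then n per arm = 2 × (1.960 + 0.842)² × 415.1 / 15² ≈ 29, which is the plan's figure. With SD 20, a t-test calculation also gives 29. The standardised in vivo difference is dy = 15/20 = 0.75.

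**Step 2: pooled correlation when the within-arm correlation is zero.** With equal arms,

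r = 0.25·dx·dy / √((1 + 0.25·dx²)(1 + 0.25·dy²)).

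- dx = 0.5: 0.0938 / √(1.0625 × 1.1406) = 0.085
- dx = 1: 0.1875 / √(1.25 × 1.1406) = 0.157
- dx = 2: 0.375 / √(2 × 1.1406) = 0.248
- dx = 0: zero
- dx = −1: −0.157

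Using SD 22.5 (dy = 0.67), r runs from 0.08 to 0.22 over dx 0.5 to 2. Using SD 18 (dy = 0.83), it runs from 0.09 to 0.27.

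**Step 3: false-positive rate per correlation** (simulated, two-sided nominal 5%, dy = 0.75):

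| Cultures in the stratum | dx = 0.5 | dx = 1 | dx = 2 |
|---|---|---|---|
| 10 | about 6% | about 7% | about 11% |
| 20 | about 7% | about 10% | about 19% |
| 32 | about 7% | about 14% | about 29% |

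Spearman gave nearly the same rates as Pearson where both were run (20 and 32 cultures). At dx = 0 the rate stays near 5%.

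**Step 4: the same data adjusted for arm.** The partial correlation averages about zero, and its false-positive rate is about 5% in every setting.

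**Step 5: the opposite error.** If the culture difference ran the other way by 1 SD, a true within-arm correlation of 0.40 would appear as (0.40 − 0.1875) / √(1.25 × 1.1406) = 0.18 when pooled.

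**The case against.** The strongest reply is that nothing in the text says the arms are combined. The objective names the two drugs, each assay uses the patient's own drug, and the neighbouring gene-signature analysis is done by drug. An analyst could correlate drug by drug without contradicting the plan. This stands in part: drug is left out of the correlation rather than expressly excluded. But menopausal status is the only split named, and the authors wrote by-drug wording one paragraph earlier when they wanted it. Pooling remains the plain reading.

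Second, the direction is uncertain. The evidence on sensitivity comes from laboratory work on cyclin D1 overexpressing cells. Correlative Laboratory Research takes culture tissue from the surgical specimen, after treatment with the same drug, and the documents do not say whether such cells would show the same contrast. This stands, and it is why the results include a nil and a reversed difference.

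Third, the aim is secondary and opportunistic, and the plan calls it proof of principle. No significance threshold is set for these correlations, so 5% is only a yardstick. That limits the weight of the point, but the stated validation claim keeps it worth correcting.

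A reader might go further and infer false-positive rates of a third or a half, by putting 40 or more cultures into one correlation or by assuming drug differences of several SDs in culture. The documents do not support that. The correlation is split by menopausal status in a trial of 64, cultures come from only a subset, and no culture difference of any size is given.

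**Conclusion.** The concern holds, at moderate size. Read plainly, the correlation pools the two drugs. If the cultures differ by drug in the direction that the plan's rationale suggests, the pooled result is biased upwards by about 0.09 to 0.25. The false-positive rate per correlation then lies between about 6% and 29%, depending on the number of cultures in a stratum and on a culture difference that has to be assumed.

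It would be too strong to say that the plan commits itself to pooling, or that a positive correlation would necessarily be spurious. The first is implied by what the text omits, and the second depends on a difference that may be absent or reversed. The primary Ki67 comparison is unaffected. The change should still be made, because the validation claim concerns patient-level prediction and the pooled statistic does not isolate it.

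**What to change.** State in Data Analysis that treatment arm is taken into account in this correlation, in one of two ways:

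- within each menopausal stratum, report the partial correlation adjusted for arm, on ranks if the data are not normally distributed; or
- fit one regression of Ki67 change on culture response, with terms for arm and menopausal status.

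In either case, standardise the culture read-out within drug, and base any statement that organoid culture predicts patient response on the arm-adjusted estimate alone.

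Do not rely on four separate correlations by arm and menopausal status. With equal strata and 20 to 40 cultures in all, each cell would hold 5 to 10 patients. At n = 10, an observed correlation of 0.5 has a 95% interval of tanh(0.549 ± 1.96/√7), or about −0.19 to 0.86.

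The cost is a sentence or two of text and one or two degrees of freedom. No new data are needed.

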Following examination by the study pathologist of the Ki67 immunohistochemically stained sections and an additional section stained with H&E, areas of viable tumor tissue within the cores will be identified, the extent of antibody staining assessed using appropriate protocols for digital image capture and analysis. It is our expectation that the cores will show considerable intratumoral heterogeneity in the extent of staining and that individual strongly staining nuclei may be interspersed among weakly or negatively stained cells. In order to address the problem of intratumoral heterogeneity, we will obtain digital images of the entire tissue section and determine the number of positively stained nuclei per 100,000 μm^2 of viable tumor tissue.

In addition, manual scoring of cyclinD1, STAT3, STAT5 and Ki67 will also be performed. The manual scoring will be performed as described previously where a score for percentage of cells stained and a score for intensity of scoring is obtained and then added to obtain an Allred score.

For the ER, we predict that pre-treatment specimens from both arms will show evidence of ER staining in the nucleus. In post-treatment specimens, the fulvestrant alone arm will show reduced nuclear staining of ER and some cytoplasmic staining of ER. The staining of ER will be assessed with the 6F11 monoclonal antibody (Vision Biosystem) as this is the antibody used clinically at this time. Intensity will be scored (0, 1+, 2+, 3+) by the level of staining in the nucleus and cytoplasm. ER will also be expressed as a percentage (0-100%) of cells staining positive within the breast tumor.

For the PR, we predict that pre-treatment specimens from both arms will show evidence of PR staining in the nucleus. In post-treatment specimens, the fulvestrant alone arm will show reduced staining of PR given the downregulation of the ER by fulvestrant. Intensity will be scored (0, 1+, 2+, 3+). PR will also be expressed as a percentage (0-100%) of cells staining positive within the breast tumor.

Tunel assay will be used to determine the percentage of cells that underwent apoptosis. Paraffin embedded sections will be stained using the apoptosis detection kit TACS-KL Basic (TA100, R&D systems Inc, Minneapolis) according to the manufacturer's protocol. Sections will be counterstained with 0.2% hematoxylin to detect intact nuclei. Our data suggest that more apoptotic cells will be detected in

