The principal investigator and study coordinator will be responsible for data accuracy and completeness. Subjects will be monitored for side effects of study medication, medication compliance, and birth control practices/pregnancy. Data will be collected electronically using Mount Sinai's secure Web-based Electronic Research Application Portal (ERAP).

Safety and data information will be reviewed by the PI and attending breast physicians at Dubin Breast Center and Mount Sinai St. Luke's. as per routine standard care procedures for post breast cancer surgical patients and ongoing laboratory testing procedures and data collection as described in the protocol.

Subjects will only receive only one cycle of study medication. Afterward they will receive treatment with surgery and postsurgical follow-up as their conditions warrant.

Subjects will be evaluated for side effects using the CTC criteria version 4.0. If a temporary or permanent suspension of our study occurs, we will notify the IRB at once.

The principal data and safety monitor will be the PI, [name]. The co-investigator who will also oversee data and safety monitoring will be [name]. Both of these physicians routinely care for cancer patients being treated with endocrine therapies and both have experience conducting clinical research.

Definitions

Definition of adverse event

An adverse event is the development of an undesirable medical condition or the deterioration of a pre-existing medical condition following or during exposure to a pharmaceutical product, whether or not considered causally related to the product. An undesirable medical condition can be symptoms (eg, nausea, chest pain), signs (eg, tachycardia, enlarged liver) or the abnormal results of an investigation (eg, laboratory findings, electrocardiogram). In clinical studies, an AE can include an undesirable medical condition occurring at any time, including run-in or washout periods, even if no study treatment has been administered. The term AE is used to include both serious and non-serious AEs.

Definitions of serious adverse event

A serious adverse event is an AE occurring during any study phase (ie, run-in, treatment, washout, follow-up), that fulfills one or more of the following criteria:

- Results in death
- Is immediately life-threatening
- Requires in-patient hospitalization or prolongation of existing hospitalization

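### Does the missing unit on the 50% and 25% Ki67 stopping thresholds leave the arm-stopping rules unsettled?

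*Combined protocol and SAP*

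**What the plan says.** The Statistical Analysis Plan (Stopping Rule) sets two rules for each arm.

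- **Mean rule.** It acts if the mean change from baseline in the Ki67 index "among the first fourteen patients in the tamoxifen arm is an increase of at least 25"%. The plan adds an 80% confidence interval under which "the true mean Ki67 increase in a treatment arm is in the range of 16% to 34"%.
- **2-of-10 rule.** It is introduced as "based on the number of patients experiencing a high level of proliferation (50% or higher"). It acts if 2 of the first 10 patients in an arm "experience an increase from baseline in the Ki67 proliferation index of 50% or more, then that treatment arm will be terminated".

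Both rules are repeated under Removal of Patients from Therapy and Removal of Subjects, with the same thresholds and the same trigger sentence for the 2-of-10 rule. One word of consequence differs for the mean rule. The SAP says the arm is terminated, while the other two sections say recruitment to it is stopped.

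On units, the SAP's primary endpoint is the change in proliferation index "as measured by the percentage of cells staining for Ki67 in each treatment arm". The sample size is set to "detect a difference between treatments of 15% in cells staining for Ki67". Laboratory Determinations and Pathology Review also describes a digital readout, "the number of positively stained nuclei per 100,000" square micrometres of viable tumour.

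**The concern.** Two adjacent sentences describe the 2-of-10 rule differently, one by a level and one by a rise. Neither rule names its unit, and the possible readings count different patients. Someone starting at 10% Ki67 counts from 10 + 50 = 60% upward if the rise is in points, but from 10 × 1.5 = 15% upward if it is relative. Someone going from 40% to 52% reaches the introductory level but satisfies neither version of the rise. Someone starting above 50% can never rise by 50 points.

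Two such classifications among ten patients can close one arm of a two-arm randomised comparison. The rules exist because the protocol takes seriously the possibility that tamoxifen speeds growth in these tumours, so a trigger that different people could apply differently deserves a check.

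**Working it through.** **Inputs.** From the opening paragraph of the SAP: SDs of Ki67 change 22.5 (fulvestrant 250 mg) and 18.0 (placebo), planned mean changes −5 (tamoxifen) and −20 (fulvestrant), difference 15, power 0.80, two-sided 0.05. From Stopping Rule: 14 patients with interval 16 to 34, and 2 of 10 patients with threshold 50.

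**1. Which sentence operates.** The introductory phrase says what kind of rule follows. The conditional sentence after it carries the count, the comparison with baseline and the consequence, and it is the same in all three sections. The level reading therefore has no operative text behind it.

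**2. The unit of the index.** Both rules refer to the Ki67 proliferation index, which the endpoint defines as the percentage of cells staining. The SAP's Data Analysis section models post-treatment percentage with baseline percentage as covariate. No section expresses a Ki67 change relative to baseline. The sample size confirms the scale:

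- SD = √[(22.5² + 18.0²)/2] = 20.37. The plan does not state which SD it used, so this one is inferred.
- n per arm = 2 × (1.960 + 0.842)² × 20.37² / 15² = 28.96, so 29 by the normal approximation, which is the plan's figure.

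**3. The interval attached to the mean rule.** At 80% with SD 20.37, the half-width is 1.2816 × 20.37/√14 = 6.98, giving 18.0 to 32.0 (17.6 to 32.4 with t). With SD 22.5 the interval is 17.3 to 32.7 (z) or 16.9 to 33.1 (t). None of these is 16 to 34. At 90% with SD 20.37, the half-width is 1.645 × 20.37/√14 = 8.96, giving 16.0 to 34.0. The stated interval thus fits the SD that reproduces the sample size, in points, if 80% is a slip for 90%. Keeping 80% needs an SD of 24.9 (t) or 26.3 (z), which appears nowhere in the documents. This is a supporting hint only.

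**4. Behaviour of the 2-of-10 rule in points.** For normal changes, p = 1 − Φ[(50 − μ)/SD], and the chance of closure is P = 1 − (1 − p)¹⁰ − 10p(1 − p)⁹.

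| Planned mean | SD | p | P(arm closed) |
|---|---|---|---|
| −5 (tamoxifen) | 20.37 | 0.0035 | 0.0005 |
| −5 (tamoxifen) | 22.5 | 0.0073 | 0.0023 |
| −20 (fulvestrant) | 20.37 | 0.0003 | 0.000004 |
| −20 (fulvestrant) | 22.5 | 0.0009 | 0.00004 |

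If the true mean change were 0, P would be 0.0022 (SD 20.37) or 0.0072 (SD 22.5). Even at the SDs of 24.9 and 26.3 from step 3, the tamoxifen figure is 0.0079 to 0.0135. For the mean rule, a true mean change of 0 and SD 20.37 give a chance of about 0.000002 of reaching 25 points in 14 patients.

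**5. Terminated against recruitment stopped.** Each patient has a single 14-day cycle, and fulvestrant is given once, on day 1. At about 20 enrolments a year (Sample Size and Accrual), or about 10 per arm, the average number in the treatment window is 10 × 14/365 ≈ 0.4 per arm. The two wordings would rarely apply to different patients.

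**The case for a change.** The strongest case against leaving this alone is that a safety rule should not depend on inference. No sentence in any of the three sections states the unit, and the one figure attached to the rules does not reproduce as labelled. The trial is unblinded, and "The principal data and safety monitor will be the PI", so an unstated unit could be settled by someone who sees results by arm. The readings can also diverge widely. With a normal model at SD 20.37 and an assumed common baseline of 30% or 40%, a relative reading would close the planned tamoxifen arm with probability 50% or 30%. A digital count of nuclei per area also has no percentage-point scale, so on that readout a 50% rise could only be relative.

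The omission itself stands, as do the two wording mismatches. The rest carries less weight:

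- The relative-reading figures need a baseline Ki67 that the documents do not give. They borrow an SD from the points scale and put 11% (baseline 30) or 4% (baseline 40) of post-treatment tamoxifen values below zero. A lognormal version with an assumed ratio of 0.75 and log-SD of 0.3 to 0.7 runs from 0.5% to 50%, which settles nothing.
- The nuclei count is offered to handle heterogeneity within the tumour. It is tied to neither the endpoint definition nor a stopping rule.
- Monitoring does not rest on one person. A co-investigator shares oversight, attending breast physicians review the data, and a study pathologist determines Ki67. That the unit would be chosen after seeing results is conjecture.

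**Conclusion.** This is a gap that an analyst following the plan fills from the plan itself, together with a clerical mismatch in wording. The endpoint's own unit, the Data Analysis section and the reproduced sample size all point to percentage points of cells staining. In that unit the 2-of-10 rule closes a tamoxifen arm behaving as planned with probability 0.05% to 0.23%, and a fulvestrant arm with probability below 0.01%. These figures assume normal changes and SDs of 20.37 to 22.5. No fault in either threshold has been shown. Whether rules this hard to trigger are the right safeguard is a separate clinical judgement, and nothing here decides it.

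The level and rise sentences, and the terminated and recruitment-stopped wordings, do disagree across the three sections and must be reconciled editorially, with the choice left to the investigators. That has no demonstrated effect on any result and alters no patient number, procedure or analysis.
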